#### 5.2.1 Eligible cohort entry date

Sacubitril/valsartan was approved by FDA for market availability on July 7, 2015.

- Optum: July 7, 2015 – March 31, 2020 (end of data availability)
- Marketscan: July 7, 2015 – December 31, 2018 (end of data availability)
- Medicare: July 7, 2015 – December 31, 2017 (end of data availability)

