## 9. Balance Assessment

Optum- <https://bwh-dope.aetion.com/projects/details/1069/results/63131/result/0>

MarketScan- <https://bwh-dope.aetion.com/projects/details/1072/results/63129/result/0>

Medicare- <https://bwh-dope.aetion.com/projects/details/1073/results/63128/result/0>

Date conducted: 12/22/2020

After review of initial feasibility and power analyses, complete creation of the remaining covariates from Section 6.2. Again, using the

dummy outcome of a 90-day gap in database enrollment, complete a 1:1 PS-matched analysis. The PS should include the complete list of covariates.

- Provide plot of PS distributions stratified by treatment group.

Note- Please refer to **Appendix B**.

- Report covariate balance after matching.

Note- For Table 1, please refer to **Appendix B**.

- Report reasons for censoring by treatment group.

	Overall	Referent	Exposure
Dummy outcome	0 (0%)	0 (0%)	0 (0%)
Death	150 (2.47%)	64 (2.11%)	86 (2.84%)
Start of an additional exposure	309 (5.09%)	106 (3.49%)	203 (6.69%)
End of Index Exposure	2285 (37.67%)	1206 (39.76%)	1079 (35.58%)
Specified date reached	1868 (30.79)	879 (28.98%)	989 (32.61%)
End of patient enrollment	696 (11.47%)	366 (12.07%)	330 (10.88%)
Switch to ARBs or Aliskiren + Nursing Home admission Occurred	758 (12.50%)	412 (13.58%)	346 (11.41%)

- Report follow-up time by treatment group.

Patient Group	Optum Median Follow-Up Time (Days) [IQR]	MarketScan Median Follow-Up Time (Days) [IQR]	Medicare Median Follow-Up Time (Days) [IQR]
Overall Patient Population	118 [58, 286]	139 [59, 296]	102 [46, 189]
Referent - ACE Inhibitors	126 [60, 309]	142 [77, 295]	102 [42, 170]
Exposure - Sacubitril/Valsartan	108 [56, 266]	136 [58, 300]	106 [58, 218]

- Report overall risk of the primary outcome.

	Optum	MarketScan	Medicare	Pooled
Risk per 1,000 patients	206.6	160.3	248.0	215.3

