...Unknown/missing; n (%)	16 (0.1%)	3 (0.1%)	0.0000	14 (0.1%)	1 (0.1%)	0.0000						
Calendar time - Year of Initiation (2015/16 - 2020)												
...2015-2016; n (%)	4,925 (28.6%)	253 (10.4%)	0.4720	6,045 (56.4%)	380 (29.5%)	0.5847	11,750 (54.2%)	607 (36.6%)	0.5743	16,691 (36.1%)	860 (16.0%)	0.4705
...2017; n (%)	3,881 (22.5%)	500 (20.6%)	0.0462	2,610 (24.3%)	438 (34.0%)	-0.2147	6,547 (35.8%)	1,051 (53.4%)	0.5743	10,424 (22.5%)	1,551 (28.9%)	-0.1469
...2018; n (%)	3,960 (23.0%)	622 (25.7%)	-0.0629	2,066 (19.3%)	471 (36.5%)	-0.3907	0 (0.0%)	0 (0.0%)	#DIV/0!	3,968 (8.6%)	622 (11.6%)	-0.0997
...2019 - 2020; n (%)	4,468 (25.5%)	1,049 (43.3%)	-0.3721	0 (0.0%)	0 (0.0%)	#DIV/0!	0 (0.0%)	#DIV/0!		4,468 (9.7%)	1,049 (19.5%)	-0.2802
Combined comorbidity score, 180 days												
...mean (sd)	5.30 (2.55)	5.29 (2.40)	0.0040	4.21 (2.23)	4.21 (2.12)	0.0000	5.30 (2.72)	4.75 (2.39)	0.2148	5.05 (2.55)	4.86 (2.33)	0.0778
...median [IQR]	5.00 [3.00, 7.00]	5.00 [3.00, 7.00]	0.0000	4.00 [3.00, 5.00]	4.00 [3.00, 5.00]	0.0000	5.00 [3.00, 7.00]	4.00 [3.00, 6.00]	0.3906	4.77 (2.55)	4.45 (2.33)	0.1310
CV Comorbidity - Pulmonary hypertension/Other pulmonary heart disease; n (%)	2,893 (16.8%)	506 (20.9%)	-0.1050	1,274 (11.9%)	218 (16.9%)	-0.1428	3,611 (19.7%)	369 (22.3%)	-0.0639	6,504 (14.1%)	875 (16.3%)	-0.0613
CV Comorbidity - Other dysrhythmias; n (%)	9,611 (55.7%)	1,383 (57.1%)	-0.0282	5,648 (52.7%)	685 (53.1%)	-0.0080	9,911 (54.1%)	854 (51.5%)	0.0521	19,522 (42.2%)	2,237 (41.6%)	0.0122
CV Comorbidity - Valve disorder; n (%)	2,246 (13.0%)	442 (18.2%)	-0.1437	657 (6.1%)	80 (6.2%)	-0.0042	2,921 (16.0%)	323 (19.5%)	-0.0917	5,167 (11.2%)	765 (14.2%)	-0.0902
CV Comorbidity - Hospitalization for heart failure; n (%)	13,310 (77.2%)	1,891 (78.0%)	-0.0192	8,185 (76.3%)	971 (75.3%)	0.0234	15,029 (82.1%)	1,198 (72.3%)	0.2352	28,339 (61.2%)	3,089 (57.5%)	0.0754
CV Comorbidity - Implantable cardioverter defibrillator; n (%)	4,746 (27.5%)	641 (26.4%)	0.0248	2,170 (20.2%)	319 (24.7%)	-0.1080	2,292 (12.5%)	249 (15.0%)	-0.0726	7,038 (15.2%)	890 (16.6%)	-0.0383
CV Comorbidity - Hypotension; n (%)	2,300 (13.3%)	294 (12.1%)	0.0306	1,109 (10.3%)	112 (8.7%)	0.0546	3,148 (17.2%)	235 (14.2%)	0.0825	5,448 (11.8%)	529 (9.8%)	0.0645
CV Comorbidity - Hypertension; n (%)	15,907 (92.2%)	2,298 (94.8%)	-0.1056	9,139 (85.2%)	1,440 (88.4%)	-0.0946	17,177 (93.8%)	1,591 (96.0%)	-0.1001	33,084 (71.5%)	3,889 (72.4%)	-0.2000

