Calendar Time - Year of Initiation (2015/16 - 2020)	...2015-2016; n (%)	146 (11.4%)	153 (12.0%)	-0.0187	229 (30.6%)	233 (31.1%)	-0.0108	355 (35.3%)	374 (37.2%)	-0.0395	797 (26.3%)	785 (25.9%)	0.0091
...2017; n (%)	293 (22.9%)	280 (21.9%)	0.0240	264 (35.3%)	256 (34.2%)	0.0231	651 (64.7%)	632 (62.8%)	0.0395	293 (9.7%)	280 (9.2%)	0.0171	
...2018; n (%)	321 (25.1%)	319 (24.9%)	0.0046	255 (34.1%)	259 (34.6%)	-0.0105	0 (0.0%)	0 (0.0%)	#DIV/0!	321 (10.6%)	319 (10.5%)	0.0033	
...2019 - 2020; n (%)	519 (40.6%)	527 (41.2%)	-0.0122	0 (0.0%)	0 (0.0%)	#DIV/0!	0 (0.0%)	0 (0.0%)	#DIV/0!	519 (40.6%)	527 (41.2%)	-0.0122	
Combined comorbidity score, 180 days	...mean (sd)	5.30 (2.47)	5.27 (2.43)	0.0122	4.24 (2.12)	4.19 (2.06)	0.0239	4.77 (2.49)	4.76 (2.40)	0.0041	4.86 (2.40)	4.83 (2.33)	0.0127
...median [IQR]	5.00 [4.00, 7.00]	5.00 [3.00, 7.00]	0.0000	4.00 [3.00, 6.00]	4.00 [3.00, 5.00]	0.0000	4.00 [3.00, 6.00]	4.00 [3.00, 6.00]	0.0000	4.42 (2.40)	4.42 (2.33)	0.0000	
CV Comorbidity - Pulmonary hypertension/Other pulmonary heart disease; n (%)	250 (19.5%)	257 (20.1%)	-0.0151	132 (17.6%)	126 (16.8%)	0.0212	209 (20.8%)	223 (22.2%)	-0.0341	459 (15.1%)	480 (15.8%)	-0.0194	
CV Comorbidity - Other dysrhythmias; n (%)	735 (57.5%)	736 (57.5%)	0.0000	424 (56.7%)	409 (54.7%)	0.0403	506 (50.3%)	519 (51.6%)	-0.0260	1,241 (40.9%)	1,255 (41.4%)	-0.0102	
CV Comorbidity - Valve disorder; n (%)	254 (19.9%)	237 (18.5%)	0.0356	46 (6.1%)	49 (6.6%)	-0.0205	202 (20.1%)	203 (20.2%)	-0.0025	456 (15.0%)	440 (14.5%)	0.0141	
CV Comorbidity - Hospitalization for heart failure; n (%)	1,041 (81.4%)	1,051 (82.2%)	-0.0207	602 (80.5%)	593 (79.3%)	0.0299	743 (73.9%)	740 (73.6%)	0.0068	1,784 (58.8%)	1,791 (59.1%)	-0.0061	
CV Comorbidity - Implantable cardioverter defibrillator; n (%)	328 (25.6%)	303 (23.7%)	0.0441	170 (22.7%)	170 (22.7%)	0.0000	137 (13.6%)	145 (14.4%)	-0.0231	465 (15.3%)	448 (14.8%)	0.0140	
CV Comorbidity - Hypertension; n (%)	167 (13.1%)	169 (13.2%)	-0.0030	67 (9.0%)	73 (9.8%)	-0.0274	160 (15.9%)	150 (14.9%)	0.0277	327 (10.8%)	319 (10.5%)	0.0097	
CV Comorbidity - Hypertension; n (%)	1,206 (94.9%)	1,208 (94.4%)	-0.0043	666 (88.0%)	658 (88.0%)	0.0313	972 (96.6%)	960 (95.4%)	0.0613	2,178 (71.5%)	2,168 (71.5%)	0.0067	
CV Comorbidity - Coronary atherosclerosis and other forms of chronic ischemic heart disease; n (%)	959 (75.0%)	946 (74.0%)	0.0229	436 (58.3%)	427 (57.1%)	0.0243	780 (77.5%)	788 (78.2%)	-0.0193	1,739 (52.3%)	1,724 (52.2%)	0.0020	

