...median (IQR)	15.93 [5.74, 32.88]	18.14 [6.52, 33.73]	-0.0600	10.53 [3.58, 20.38]	12.40 [5.11, 19.94]	-0.1150	16.10 [5.26, 32.03]	18.78 [5.57, 34.95]	-0.0796	14.65 (36.11)	16.94 (26.88)	-0.0719
SES Proxy - Low income indicator; n (%)	275 (21.5%)	299 (23.4%)	-0.0455	0 (0.0%)	0 (0.0%)	#DIV/0!	0 (0.0%)	0 (0.0%)	#DIV/0!	275 (9.1%)	299 (9.9%)	-0.0273
SES Proxy - Business type												
...Commercial; n (%)	325 (25.4%)	340 (26.6%)	-0.0274	0 (0.0%)	0 (0.0%)	#DIV/0!	0 (0.0%)	0 (0.0%)	#DIV/0!	325 (10.7%)	340 (11.2%)	-0.0160
...Medicare; n (%)	954 (74.6%)	939 (73.4%)	0.0274	0 (0.0%)	0 (0.0%)	#DIV/0!	0 (0.0%)	0 (0.0%)	#DIV/0!	954 (31.5%)	939 (31.0%)	0.0108
SES Proxy - Insurance Plan type												
...Comprehensive; n (%)	0 (0.0%)	0 (0.0%)	#DIV/0!	105 (14.0%)	94 (12.6%)	0.0412	0 (0.0%)	0 (0.0%)	#DIV/0!	105 (3.5%)	094 (3.1%)	0.0224
...HMO; n (%)	0 (0.0%)	0 (0.0%)	#DIV/0!	62 (8.3%)	71 (9.5%)	-0.0422	0 (0.0%)	0 (0.0%)	#DIV/0!	062 (2.0%)	071 (2.3%)	-0.0207
...PPD; n (%)	0 (0.0%)	0 (0.0%)	#DIV/0!	403 (53.9%)	400 (53.5%)	0.0080	0 (0.0%)	0 (0.0%)	#DIV/0!	403 (13.3%)	400 (13.2%)	0.0029
...Others; n (%)	0 (0.0%)	0 (0.0%)	#DIV/0!	178 (23.8%)	183 (24.5%)	-0.0164	0 (0.0%)	0 (0.0%)	#DIV/0!	178 (5.9%)	183 (6.0%)	-0.0042
SES Proxy - Dual status code (with Medicaid); n (%)	0 (0.0%)	0 (0.0%)	#DIV/0!	0 (0.0%)	0 (0.0%)	#DIV/0!	202 (20.1%)	203 (20.2%)	-0.0025	202 (6.7%)	203 (6.7%)	0.0000

\*Excluded from P5 model: Age Categories, Use of Lithium, Use of AGI & Meglitinides, PCSK9 Inhibitors, Use of heparin or LMWH, Hemodialysis/Peritoneal dialysis

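### Calendar time enters the propensity score only in year bins, the first about 18 months long from approval, so balance on start date within bins is neither secured nor shown

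*Protocol*

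**What the plan says.** Section 5.2.1 opens cohort entry at approval: "Sacubitril/valsartan was approved by FDA for market availability on July 7, 2015". Entry then runs to the end of each database: "Optum: July 7, 2015 – March 31, 2020 (end of data availability"), "Marketscan: July 7, 2015 – December 31, 2018 (end of data availability") and "Medicare: July 7, 2015 – December 31, 2017 (end of data availability").

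Section 9 puts the full covariate list into the PS. Appendix B lists calendar time before matching as "Calendar time - Year of Initiation (2015/16 - 2020") and after matching as "Calendar Time - Year of Initiation (2015/16 - 2020"), with rows for 2015-2016, 2017, 2018 and 2019-2020. No monthly, quarterly or continuous version appears. The Appendix B footnote on omitted variables begins "Excluded from P5 model: Age Categories, Use of Lithium" and does not name calendar time, so the binned variable is in the model. Age is listed both as continuous and in categories, and the footnote removes the categories.

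After matching, the printed standardized differences for the calendar bins are at most 0.0395 in absolute value in any single database.

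**The concern.** A PS with bin indicators can balance the number of patients in each bin, but not where in the bin they start. That matters when one arm's entry rate changes inside the bin and the other's does not. A drug's first months on the market are the clearest case: new use starts at zero on the approval date, while ACE inhibitor initiation has no such constraint. If start dates differ between matched arms, any drift over calendar time in care or in outcome hazard is carried into the comparison, and the balance table will not show it.

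**Working it through.** **Bin lengths (Section 5.2.1).** 7 July 2015 to 31 December 2016 is 544 days (17.9 months). 2017 and 2018 are 365 days each. 1 January 2019 to 31 March 2020 is 456 days (15.0 months).

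**Reproducing the printed balance.** With d = (p1 − p2)/√[(p1q1 + p2q2)/2] and the matched counts:

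- Optum: −0.017, 0.024, 0.004, −0.013 (printed −0.0187, 0.0240, 0.0046, −0.0122)
- MarketScan: −0.012, 0.023, −0.011 (printed −0.0108, 0.0231, −0.0105)
- Medicare: −0.039, 0.039 (printed −0.0395, 0.0395)

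These agree within rounding.

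**Pooled calendar rows.** The printed 2015-2016 counts, 797/785, equal Optum 2015-2016 plus Medicare 2017 (146 + 651 and 153 + 632). The pooled 2017 and 2018 rows are Optum alone. The 2019-2020 percentage, 40.6%, is 519/1,279 rather than 519/3,033. Correct sums are:

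| Bin | ACE inhibitor | Sacubitril/valsartan | d |
|---|---|---|---|
| 2015-2016 | 146 + 229 + 355 = 730 | 153 + 233 + 374 = 760 | −0.023 |
| 2017 | 293 + 264 + 651 = 1,208 | 280 + 256 + 632 = 1,168 | 0.027 |
| 2018 | 321 + 255 = 576 | 319 + 259 = 578 | −0.002 |
| 2019-2020 | 519 | 527 | −0.007 |

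**Uptake across bins.** Share = exposed/(exposed + comparator), from the pre-match counts (some printed Medicare percentages do not match their counts, so counts are used):

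- Optum: 253/5,178 = 4.9%, then 11.4%, 13.6%, 19.0% (3.9-fold)
- MarketScan: 380/6,425 = 5.9%, then 14.4%, 18.6% (3.1-fold)
- Medicare: 607/12,357 = 4.9%, then 13.8% (2.8-fold)

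**Lag within the launch bin, first assumption.** Total initiations are even over the bin, and the share rises linearly from zero to twice its mean s. The mean start is 2L/3 for the exposed and L(1/2 − 2s/3)/(1 − s) for comparators, so the lag is L/[6(1 − s)]. With L = 544, L/6 = 90.7 days:

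- Optum: 90.7/0.951 = 95 days
- MarketScan: 90.7/0.941 = 96 days
- Medicare: 90.7/0.951 = 95 days

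**Lag within the launch bin, second assumption.** Each arm's monthly entry rate is linear, with the slope between the first two bin means. Each arm's shift is slope × L²/(12 × rate). This gives 1.9 months in MarketScan and 3.1 in Medicare. In Optum it gives 3.1, but that slope implies a negative exposed rate at launch; capping the exposed shift at L/6 gives 2.7. Together the two assumptions give about 2-3 months.

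**Other bins.** With b the average slope of the share between neighbouring bin midpoints, lag = bL²/[12s(1 − s)]. Optum 2017: b = 0.000101 per day, so 0.000101 × 365²/12 ÷ (0.114 × 0.886) = 11 days. Over all databases the lag is 11-18 days in 2017, 8-9 in 2018 and 15 in 2019-2020.

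**Overall, under the first assumption.** Weighting by the matched bin mix and adding the small between-bin difference:

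- Optum: 22.0 + 1.8 = 24 days (about 0.05 SD of start date)
- MarketScan: 37.4 − 0.5 = 37 days (about 0.10 SD)
- Medicare: 46.2 − 8.6 = 38 days (about 0.15 SD)
- Pooled: about 32 days

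The SDs assume even spread within bins.

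**Effect on the hazard ratio.** If the hazard falls by a fraction r per year, a lag of D days multiplies the ratio by (1 − r)^(D/365.25). For r = 2% and D = 15 this is 0.999. For r = 10% and D = 50 it is 0.986. The shift is thus about 0.1-1.4%. The protocol gives no drift, so both ranges are assumptions.

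**Age.** Matched Optum age 18-54 is 137/1,279 (10.7%) vs 196/1,279 (15.3%): d = −0.137 and z = 0.0461/0.0133 = 3.5, although mean age differs by only 0.064 SD. The printed MarketScan difference is +0.0764 and the pooled one −0.0291.

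**The case against.** The strongest reply is that year-of-initiation bins are a defensible choice, that they balance well in each database, and that no within-bin dates are given, so a lag is inferred rather than observed. That stands. The lag figures also apply pre-match entry rates to comparators selected on a full PS, who are not a random draw from the pool.

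A reader might take the Section 9 censoring table as proof of the lag: "Specified date reached" ends follow-up for 989 of 3,033 exposed against 879 of 3,033 comparators (32.6% vs 29.0%, z = 3.1). It does not prove it. After the launch bin closes, data run for another 365 days (Medicare), 730 (MarketScan) or 1,186 (Optum). Upper-quartile matched follow-up is only 170-218, 295-300 and 266-309 days, so few launch-bin patients can reach the data end. The exposed also have 127 fewer discontinuations, 66 fewer ARB, aliskiren or nursing-home events and 36 fewer enrolment ends, so better persistence could produce the whole gap. Median follow-up is mixed: exposed vs comparator is 108 vs 126 days in Optum and 136 vs 142 in MarketScan, but 106 vs 102 in Medicare.

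A reader might also link early entry to the change from ICD-9 to ICD-10 coding. Appendix A gives code lists in both systems but no changeover date, so the number of patients affected cannot be derived.

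On age, opposite signs in Optum and MarketScan do not show a systematic error of functional form. That age enters as a single linear term is an inference from the footnote. The Optum imbalance itself is printed.

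**Conclusion.** The point holds as a weakness of the PS specification and of its balance check, not as a demonstrated imbalance. Start date is controlled only in bins of 12 to 18 months while relative uptake rises steeply, and in the 2015-2016 bin exposed use has to start from zero. A later start among matched initiators is therefore probable: about 2-3 months in that bin (24% of matched comparators) and 1-3 weeks elsewhere, if uptake is roughly linear. The table as printed cannot settle it.

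The consequence for the hazard ratio is probably small. Even a 1.4% shift is about a quarter of a standard error: the 1,306 expected events in the Final Power Assessment give SE(log HR) ≈ 2/√1,306 = 0.055. The case for acting is that the data are already held and the matching is still being run on a dummy outcome. The misadded pooled rows are a plain error. The Optum age imbalance is a separate, smaller point of the same kind.

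**What to change.** Before any outcome analysis, replace the four calendar bins in the PS with calendar quarter of the index date, or a spline of it. Model age with a spline or with the categories now omitted. Re-match, report balance on index date in days by database (with the 2015-2016 bin shown separately), and correct the pooled calendar rows to 730/760, 1,208/1,168, 576/578 and 519/527 with percentages on 3,033.

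The cost is recoding two covariates, one more run of the match, and updated balance and power tables. No new data are needed. Some matched pairs may be lost; the number cannot be known until the match is re-run.

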### 5.2 Important steps for cohort formation

New users (defined as no use of sacubitril/valsartan in 180 days prior to index date) of the exposure will be identified. New users of a comparator drug were identified as patients with no ACEi fills during the 60 days prior to the index date to allow for patients who are switching among ACEi drugs or restarting ACEi after a brief lapse.

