### 5.3 Flowchart of the study cohort assembly

	Optum		MarketScan		Medicare*	
	Less Excluded Patients	Remaining Patients	Less Excluded Patients	Remaining Patients	Less Excluded Patients	Remaining Patients
All patients		77,673,639		200,203,908		23,466,175
Did not meet cohort entry criteria	-73,445,846	4,227,793	-196,533,760	3,670,148	-18,348,713	5,117,462
Excluded due to insufficient enrollment	-623,954	3,603,839	-340,051	3,330,097	-1,288,867	3,828,595
Excluded due to prior use of referent	-3,168,921	434,918	-2,967,886	362,211	-3,495,789	332,806
Excluded due to prior use of exposure	-29,778	405,140	-12,511	349,700	-33,013	299,793
Excluded because patient qualified in >1 exposure category	-8	405,132	-3	349,697	-9	299,784
Excluded based on Age	0	405,132	-1	349,696	0	299,784
Excluded based on Gender	-39	405,093	0	349,696	0	299,784
Excluded based on Inclusion #1 - Age >=18 years old	-624	404,469	-1,354	348,342	-721	299,063
Inclusion #3 - HFpEF prediction algorithm applied to reference group†	-381,531	22,938	-337,242	11,100	-259,816	39,247
Excluded based on Inclusion #4b - Hospitalization for HF within the last 12 months	-9,321	13,617	-4,618	6,482	-10,685	28,562
Excluded based on Inclusion #5a - ACEis or ARBs	-1,224	12,393	-385	6,097	-1,534	27,028
Excluded based on Inclusion #5b - Beta-blockers	-673	11,720	-248	5,849	-2,128	24,900
Excluded based on Exclusion #3 - Known history of angioedema	-56	11,664	-29	5,820	-200	24,700
Excluded based on Exclusion #4 - Treatment with both ACEis AND ARBs	-15	11,649	-9	5,811	-34	24,666
Excluded based on Exclusion #5 - Acute decompensated HF	-1,060	10,589	-435	5,376	-5,457	19,209
Excluded based on Exclusion #6 - Symptomatic hypotension	-734	9,855	-240	5,136	-1,964	17,245
Excluded based on Exclusion #7 - Low eGFR / renal dysfunction	-1,064	8,791	-403	4,733	-2,833	14,412
Excluded based on Exclusion #8 - Hyperkalemia	-57	8,734	-14	4,719	-116	14,296
Excluded based on Exclusion #9 - ACS, Stroke, TIA, CABG, PCI, Other CV Procedures, Carotid Angioplasty	-765	7,969	-546	4,173	-2,912	11,384
Excluded based on Exclusion #11 - Implantation of CRT device	-41	7,928	-19	4,154	-1,550	9,834
Excluded based on Exclusion #12 - History of heart transplant or LVAD	-56	7,872	-33	4,121	-35	9,799
Excluded based on Exclusion #13 - History of severe pulmonary disease	-463	7,409	-205	3,916	-1,029	8,770
Excluded based on Exclusion #14 - Diagnosis of peripartum- or chemotherapy-induced cardiomyopathy	-38	7,371	-34	3,882	-60	8,710

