### 6.2 Preliminary Covariates:

- Age

- Sex
- Combined Comorbidity Index (CCI), measured over the default baseline covariate assessment period of 180 days prior to and including the index prescription date

Covariates listed above are a small subset of covariates that will ultimately be controlled in the design and analysis phase of the study. They are included in the preliminary assessment to determine the presence of adequate overlap between the two population of patients to proceed to the next phase of the study. Remaining covariates are defined only after the study has passed the initial feasibility analysis and initial power assessment and are listed in Table 1 (**Appendix B**).

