# Appendix A

		Measured 365 days prior to drug initiation in any diagnosis position and inpatient care setting	
4b	Hospitalization for heart failure within the last 12 months	
Hospital Admission for CHF
 
ICD-9 diagnosis: 428.x, 398.91, 402.01, 402.11, 402.91, 404.01, 404.11, 404.91, 404.03, 404.13, 404.93
 
ICD-10 diagnosis: I50.1, I50.2x, I50.4, I50.814, I09.81, I11.0, I13.0, I13.2
	
5	Treatment with a stable dose of an ACE inhibitor or an ARB equivalent to enalapril 10 mg/day for at least 4 weeks before the screening visit; and treatment with a stable dose of a beta-blocker for at least 4 weeks prior to the screening visit, unless contraindicated or not tolerated	
Measured 47 days to 2 days prior to drug initiation in prescription claims requiring 28 days supply of oral ACEi or ARB -
 
ACE inhibitors' generic names for prescription claims: Enalapril, Captopril, Clazapril, Fosinopril, Lisinopril, Moexipril, Perindopril, Quinapril, Trandolapril, Zofenopril, Benazepril
 
-OR-
 
ARBs generic names for prescription claims: Candesartan, Eprosartan, Irbesartan, Losartan, Olmesartan, Telmisartan, Valsartan, Azilsartan
	
5a	Treatment with a stable dose of an ACE inhibitor or an ARB equivalent to enalapril 10 mg/day for at least 4 weeks before the screening visit	AND the following:	
5b	Treatment with a stable dose of a beta-blocker for at least 4 weeks prior to the screening visit, unless contraindicated or not tolerated	
Measured 45 days prior to index drug initiation in prescription claims (generic names) of an oral beta-blocker for at least 4 weeks (28 days)
 
Beta-blocker generic names for prescription claims: Acebutolol, Atenolol, Betaxolol, Bisoprolol, Carvedilol, Esmolol, Labetalol, Metoprolol, Metiranolol, Nebivolol, Nadolol, Propranolol, Pindolol, Sotalol, Penbutolol, Oxprenolol
	
6	Although not required, the protocol specified that an aldosterone antagonist should also be considered in all patients, taking account of renal function, serum potassium, and tolerability. If given, the dose of aldosterone antagonist should be stable for at least 4 weeks prior to the screening visit		
EXCLUSION CRITERIA			

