Other Medication - Use of antidepressants ; n (%)	306 (23.9%)	317 (24.8%)	-0.0210	159 (21.3%)	159 (21.3%)	0.0000	284 (28.2%)	280 (27.8%)	0.0089	590 (19.5%)	597 (19.7%)	-0.0050
Other Medication - Use of lithium ; n (%)*	0 (0.0%)	0 (0.0%)	#DIV/0!	3 (0.4%)	0 (0.0%)	0.0896	2 (0.2%)	0 (0.0%)	0.0633	002 (0.1%)	000 (0.0%)	0.0447
Other Medication - Use of Benzodiazepine; n (%)	397 (15.4%)	187 (14.6%)	0.0224	92 (12.3%)	104 (13.9%)	-0.0474	131 (13.0%)	141 (14.0%)	-0.0293	328 (10.8%)	328 (10.8%)	0.0000
Other Medication - Use of opioids ; n (%)	385 (30.1%)	386 (30.2%)	-0.0022	213 (28.5%)	206 (27.5%)	0.0223	267 (26.5%)	281 (27.9%)	-0.0315	652 (21.5%)	667 (22.0%)	-0.0121
Other Medication - Use of COPD/asthma meds ; n (%)	296 (23.1%)	269 (21.0%)	0.0507	139 (18.6%)	152 (20.3%)	-0.0430	195 (19.4%)	218 (21.7%)	-0.0569	491 (16.2%)	487 (16.1%)	0.0027
HU - Bone mineral density; n (%)	28 (2.2%)	28 (2.2%)	0.0000	8 (1.1%)	9 (1.2%)	-0.0094	16 (1.6%)	14 (1.4%)	0.0165	044 (1.5%)	042 (1.4%)	0.0084
HU - Flexible Sigmoidoscopy or colonoscopy or CT virtual colonoscopy; n (%)	61 (4.8%)	55 (4.3%)	0.0240	30 (4.0%)	27 (3.6%)	0.0209	36 (3.6%)	41 (4.1%)	-0.0260	097 (3.2%)	096 (3.2%)	0.0000
HU - Flu vaccine; n (%)	235 (18.4%)	238 (18.6%)	-0.0052	76 (10.2%)	83 (11.1%)	-0.0292	306 (30.4%)	304 (30.2%)	0.0044	541 (17.8%)	542 (17.9%)	-0.0262
HU - Mammogram; n (%)	63 (4.9%)	62 (4.8%)	0.0047	36 (4.8%)	30 (4.0%)	0.0390	51 (5.1%)	46 (4.6%)	0.0233	114 (3.8%)	108 (3.6%)	0.0106
HU - Frailty Score: Empirical Version 365 days												
...mean (sd)	0.22 (0.06)	0.22 (0.06)	0.0000	0.20 (0.05)	0.19 (0.05)	0.2000	0.24 (0.07)	0.24 (0.07)	0.0000	0.22 (0.06)	0.22 (0.06)	0.0000
...median (IQR)	0.21 [0.18, 0.25]	0.21 [0.18, 0.25]	0.0000	0.18 [0.16, 0.22]	0.18 [0.16, 0.21]	0.0000	0.22 [0.19, 0.27]	0.22 [0.19, 0.27]	0.0000	0.21 [0.16, 0.26]	0.21 [0.16, 0.26]	0.0000
HU - Number of hospitalizations during CAP												
...mean (sd)	1.06 (0.77)	1.08 (0.76)	-0.0261	0.98 (0.65)	0.95 (0.66)	0.0458	1.07 (0.91)	1.07 (0.90)	0.0000	1.04 (0.79)	1.04 (0.79)	0.0000
...median (IQR)	1.00 [1.00, 1.00]	1.00 [1.00, 1.00]	0.0000	1.00 [1.00, 1.00]	1.00 [1.00, 1.00]	0.0000	1.00 [1.00, 1.00]	1.00 [0.95, 1.00]	0.0000	1.00 [0.97, 1.00]	1.00 [0.97, 1.00]	0.0000
HU - Number of Emergency Department (ED) visits												
...mean (sd)	1.81 (2.51)	1.84 (2.32)	-0.0124	2.56 (5.33)	2.40 (3.90)	0.0343	1.73 (2.19)	1.65 (2.78)	0.0320	1.97 (3.35)	1.92 (2.93)	0.0159

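### The propensity score carries prior HF admission only as a yes/no flag and a general admission count, so balance on how recently patients were discharged is neither sought nor shown

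*Protocol*

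**What the plan says.** Appendix A, Inclusion 4b, defines the qualifying HF admission as "Measured 365 days prior to drug initiation in any diagnosis position and inpatient care setting". The flowchart in Section 5.3 has a matching row, "Excluded based on Inclusion #4b - Hospitalization for HF within the last 12 months".

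Section 6.2 says the remaining covariates are those in Table 1 of Appendix B, and Section 9 adds: "The PS should include the complete list of covariates". The PS content is therefore fixed in this document. Appendix B carries admission history in two readable rows: "CV Comorbidity - Hospitalization for heart failure; n" (%) and "HU - Number of hospitalizations during CAP". The footnote beginning "Excluded from P5 model: Age Categories, Use of Lithium" names neither, so both are in the PS.

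The flag's window is not stated. For the comorbidity index, Section 6.2 gives a default: "measured over the default baseline covariate assessment period of 180 days prior to and including the index prescription date". Exclusion 5 in Appendix A removes patients with certain acute HF codes in inpatient or emergency claims from day -7 to the index day. The primary outcome in Section 6.3.1 is HF hospitalization or all-cause death.

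**The concern.** The cohort is selected on an event, an HF admission, whose recurrence is half of the primary composite. If the risk of another admission depends on time since the last discharge, that time is a prognostic baseline variable. If it also differs between arms, it confounds the comparison. The PS can adjust only for what it contains, and a flag plus a count does not order patients by recency within the flag's window.

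The primary as-treated follow-up is short, so a difference in starting position could affect a sizeable part of it. At stake is whether agreement or disagreement with the trial's HR of 0.80 can be read as a drug effect. The protocol does not state how readmission risk changes after discharge. That recency is prognostic is an assumption here, though Exclusion 5 shows that the plan already treats very recent decompensation as different.

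**Working it through.** **1. What the flag separates (Appendix B, after matching).**

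| | ACEi | Sacubitril/valsartan | St. Diff |
|---|---|---|---|
| Optum | 1,041/1,279 (81.4%) | 1,051/1,279 (82.2%) | -0.0207 |
| MarketScan | 602/748 (80.5%) | 593/748 (79.3%) | 0.0299 |
| Medicare | 743/1,006 (73.9%) | 740/1,006 (73.6%) | 0.0068 |

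Sums: (1,041 + 602 + 743)/3,033 = 2,386/3,033 = 78.7%, and (1,051 + 593 + 740)/3,033 = 2,384/3,033 = 78.6%. The printed pooled values, 58.8% and 59.1%, leave MarketScan out of the numerator: (1,041 + 743)/3,033 = 58.8%.

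That leaves 647 and 649 patients without the flag. If 4b was applied to this cohort, the flag's window must be shorter than 365 days, presumably the 180-day default. It is then one coarse recency split, with about 79% of each arm in a single unordered class.

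**2. What the count adds.** Matched means are 1.06 vs 1.08 (Optum, St. Diff -0.0261), 0.98 vs 0.95 (MarketScan, 0.0458) and 1.07 vs 1.07 (Medicare, 0.0000). The count is balanced, but it is not labelled HF-specific and does not date the admissions.

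**3. What Exclusion 5 removes (Section 5.3).**
- Optum: 1,060/11,649 = 9.1%
- MarketScan: 435/5,811 = 7.5%
- Medicare: 5,457/24,666 = 22.1%

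It reaches back only 7 days and uses five codes (428.41, 428.43, I50.23, I50.41, I50.43). The 4b list is wider and includes, for example, I11.0 and I13.0. Patients from day 8 onward stay in, as do those admitted within 7 days under other 4b codes only.

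**4. Is admission history related to treatment choice before matching?**

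| | Flag, ACEi vs sac/val | St. Diff | Mean hospitalizations | St. Diff |
|---|---|---|---|---|
| Optum | 77.2% vs 78.0% | -0.0192 | 1.06 vs 1.03 | 0.0375 |
| MarketScan | 76.3% vs 75.3% | 0.0234 | 0.96 vs 0.90 | 0.0844 |
| Medicare | 82.1% vs 72.3% | 0.2352 | 1.39 vs 1.04 | 0.3498 |

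In Medicare it is. On the flag, the other two databases show little difference.

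**5. Follow-up (Section 9, matched).** Overall medians are 118, 139 and 102 days. At 30.44 days per month, 102/30.44 = 3.4 and 139/30.44 = 4.6 months.

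**6. Room for a re-match (Final Power Assessment).** The plan's figure reproduces: events = 2 × 3,033 × 0.21525 = 1,305.7, and power = Φ(√1,305.7/2 × ln 1.25 - 1.96) = Φ(2.07) = 0.981. If 10% of pairs were lost (an assumption), events would be about 1,175 and power Φ(√1,175/2 × 0.2231 - 1.96) = Φ(1.86) = 0.97.

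**The case against.** The strongest reply is that the matched cohort is well balanced on everything the plan records about admissions, as well as on emergency visits, loop diuretics and, apart from a MarketScan difference of 0.098, cardiology visits. Some balance on recency may follow indirectly. The flag is itself probably a recency split, and Exclusion 5 trims the most recent cases. Nothing in the protocol shows an imbalance in discharge timing, and nothing in it describes how risk falls after discharge. All of this stands. It limits the claim to an unmeasured possibility but does not supply the missing check.

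Two limits of the text also stand. The Other Comorbidity and Other Medication rows are cut off in places, although the CV-comorbidity and health-use rows, where a recency variable would be expected, are readable. Appendix B also starts from 46,268 + 5,371 = 51,639 patients, against 18,671 in the flowchart, so it is not confirmed that 4b was applied to the matched set.

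A reader might infer that comparators start closer to discharge and that the HR is therefore biased towards sacubitril/valsartan. The documents do not support this. The supporting imbalance is pre-match and confined to Medicare, while Optum and MarketScan supply 1,279 + 748 = 2,027 of the 3,033 pairs. The entry rules do not settle it either. Section 5.2 lets comparators enter when "restarting ACEi after a brief lapse", but nothing links that to discharge, and the prior ACEi/ARB supply in Inclusion 5a carries no arm restriction. Appendix A also places outcome measurement 14 days after initiation, whereas Section 6.3.2 starts follow-up the next day. If the 14-day rule were applied, the earliest period would drop out.

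**Conclusion.** The gap is real but of unknown size and sign. The PS list fixed by Sections 6.2 and 9 has no readable term for time since HF discharge. About 79% of each matched arm falls in one class of the flag, and post-match differences of at most 0.05 on flag and count say nothing about order within that class. The Medicare pre-match differences show only that admission history is related to treatment there.

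The point rests on three assumptions: that 4b was applied to the matched cohort, that the flag's window is about 180 days, and that recency of discharge is prognostic for the composite. A reader might go further and conclude that a result near 0.80 would be an artefact of timing. That would need recency shares by arm and a hazard by time since discharge, and the protocol gives neither. The point merits a change before outcomes are analysed, because the variable comes from claims already used for eligibility.

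**What to change.** At the review stop in the Final Power Assessment, before any outcome analysis:

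- Confirm that 4b was applied to the cohort in Appendix B, and state the windows of the HF flag and the hospitalization count.
- Add days from last HF discharge to index to the PS covariates (Section 6.2 and Appendix B), in categories such as 0-7, 8-30, 31-90, 91-180 and 181-365.
- Report its distribution and standardized difference by arm and database, before and after matching, and re-match.
- If any category keeps an absolute standardized difference above 0.1, match exactly on it.

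The cost is one covariate derived from the 4b claims, one re-match and possibly a small loss of pairs. Pooled power would stay near 0.97 even if a tenth were lost. The single-database analyses, already at 0.41 to 0.73, would lose some power as well.
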